# **Study Schema**

1 cycle = 3 weeks (21 days) with a 2-cycle minimum unless medically contraindicated.

**HCW9218** at assigned dose by subcutaneous (SC) injection once every 3 weeks until disease progression, unacceptable toxicity, patient refusal, or felt to be no longer of benefit

Assess for Dose Limiting Toxicity (DLT) at Cycle 2 Day 1 (defined below and in Section 6.3)

tumor biopsy (baseline and prior to Cycle 3) – optional, in participants with accessible tumor who have signed the separate biopsy consent (Tumor used for biopsy should not be a RECIST target lesions unless there are no other lesions suitable for biopsy.)

Disease reassessment per disease specific standard of care (i.e. every 8-12 weeks)

Phase I HCW9218 Dose Levels			
Dose Level (DL)	HCW9218 dose		
-1*	0.1 mg/kg		
1 (start)	0.25 mg/kg		
2	0.5 mg/kg		
3	0.8 mg/kg		
4	1.2 mg/kg		

\* use only if excessive toxicity encountered at DL1

**Dose limiting toxicity (DLT)** is defined as any of the following **treatment emergent events** based on CTCAE v5 within 21 days after the 1st dose of HCW9218 as assessed on Day 22 (Cycle 2 Day 1) per Section 6.3.

DLT event	Exceptions:			
Any Grade 4 hematologic event	
 
Grade 4 lymphopenia that resolves to Grade 1 or lower (or to Baseline or lower, if pre-existing Grade 2 or higher) within 7 days
 
Grade 4 leukopenia that resolves to Grade 1 or lower (or to Baseline or lower, if pre-existing Grade 2 or higher) within 7 days
 
			
Any Grade 3 or Grade 4 febrile neutropenia				
Any Grade 3 thrombocytopenia with bleeding				
Any Grade 3 or higher non-hematologic adverse event	
 
Grade 3 nausea, vomiting and/or diarrhea that last < 72 hours
 
Grade 3 or higher electrolyte abnormality that lasts < 72 hours, is not clinically complicated, and resolves spontaneously or responds to conventional medical interventions
 
Isolated Grade 3 elevation of ALT and/or AST that resolves to Grade 1 or lower (or to Baseline or lower, if pre-existing Grade 2 or higher) within 7 days
 
Grade 3 amylase or lipase that is not associated with symptoms or clinical manifestations of pancreatitis
 
Grade 3 fatigue, not due to disease progression, that lasts < 1 week
 
			

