### 6.3 Monitoring for Dose Limiting Toxicities and Excessive Toxicity

Toxicity and adverse events are classified and graded according to NCI's Common Terminology Criteria for Adverse Events V 5.0 (CTCAE) unless otherwise noted in Section 10.

Note during the fast-track dose escalation only (Stage 1, Step 1), patients also are monitored for the pre-defined treatment emergent events defined in Section 6.2.1.

**Dose Limiting Toxicity (DLT)** is defined as any of the following treatment emergent adverse events using the NCI Common Terminology Criteria for Adverse Events (CTCAE) Version 5.0 within the 21 days after the 1st dose of HCW9218:

DLT event	Exceptions:		
Any Grade 3 or Grade 4 febrile neutropenia Any Grade 3 thrombocytopenia with bleeding Any Grade 3 or higher non-hematologic adverse event	
 
Grade 4 lymphopenia hat resolves to Grade 1 or lower (or to Baseline or lower, if pre-existing Grade 2 or higher) within 7 days
 
Grade 4 leukopenia that resolves to Grade 1 or lower (or to Baseline or lower, if pre-existing Grade 2 or higher) within 7 days
 
Grade 3 nausea, vomiting and/or diarrhea that last < 72 hours
 
Grade 3 or higher electrolyte abnormality that lasts < 72 hours, is not clinically complicated, and resolves spontaneously or responds to conventional medical interventions
 
Isolated Grade 3 elevation of ALT and/or AST that resolves to Grade 1 or lower (or to Baseline or lower, if pre-existing Grade 2 or higher) within 7 days
 
Grade 3 amylase or lipase that is not associated with symptoms or clinical manifestations of pancreatitis
 
		
	
 
Grade 3 fatigue, not due to disease progression, that lasts < 1 week
 
		
Hy's Law case (i.e., alanine aminotransferase/ aspartate aminotransferase (ALT/AST) >3 x ULN in combination with total bilirubin level (TBL) > 2 x ULN in the absence of cholestatic injury (ALP < 2 x ULN (Ricart, 2017; FDA, 2009)) and no other cause identified) after excluding biliary tract obstruction and liver metastasis  Inability to receive Cycle 2 dosing due to treatment related toxicity	MORE - I WOR		

The Dose Limiting Toxicity (DLT) Observation Period is defined as 21 days after the first dose of HCW9218. The DLT period does not end until the patient is assessed on Cycle 2 Day 1 (+3 days) and the results of lab work drawn on Cycle 2 Day 1 (+3 days) confirms no new DLTs since the previous assessment.

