#### 8.1 Standard of Care Activities

Standard of care assessments and procedures are part of good clinical care and are charged to the patient and their health insurance.

	Baseline / screening Within 28 days of Cycle 1 Day 1 unless o/w noted¹	Cycle	1					Cycle	2				Cycle 3 and subsequent cycles	Every 4 cycles (12 weeks) or per SOC if more	End of treatment (EOT) visit 3 weeks after the last dose	After EOT visit: Follow-up for response until PD, then survival only every 3 mon
Study day	-28 to -1 (no Day 0)	1	2	3	5	8	15	1	2	5	8	15	1	frequent until PD	of HCW9218	for 12 months from C1D1
window	Not applicable	±1	day us	sing Day	1 as th	ne anch	or	+3 da	ys for I	Day 1	then ±	£1 day	±3 days	± 14 days	± 1 week	± 1 month
Written consent	X1															
Assess for eligibility	Х															
Medical history including prior cancer treatment	Х															
Concomitant medications	X	Х				Χ	Χ	Χ			Χ	Χ	Х		Х	
AE assessment		Χ	Χ	Х	Χ	Χ	Χ	Χ	Χ	Χ	Χ	Χ	Х		Х	
Physical exam 	Х	Χ				Χ		Χ					Х		Х	
Provider assessment	Х	Х			Χ	Χ	Χ	Χ					Х		Х	
ECOG Performance Status	Х	Χ				Χ		Χ							Х	
Vitals signs	Х	X 3	Χ	Х	Χ	Χ	Χ	X 3	Χ	Χ	Χ	Χ	X 		Х	
Weight  plus height at baseline only	X	X 				Χ		Χ				Χ	Х		X	
CBC with differential	X1	X 	Χ	Χ	Χ	Χ	Χ	Χ	Χ	Χ	Χ	Χ	X 		X	
Complete metabolic panel 	X 	X 				Χ		Χ					X 		Х	
CRP, ferritin, amylase, lipase, LDH, mg, phos	X8					X8										
Diagnosis related biomarker (e.g., CA125, PSA)	Х													Х		Х
Pulmonary function testing only if clinically indicated	Х															
Tumor assessment by disease appropriate methods	X 													Х		Х
Disease response based on RECIST 1.1 (until disease progression)	X 													Х		Х
Survival/follow-up																Х

1. Baseline/Screening – within 14 days of study treatment start for labs required for eligibility; prior disease assessments may be used if they were performed within 42 days of the 1st HCW9218 dose in the absence of intervening anti-cancer therapy. Consent is exempt from 28 day limit and may be performed at any time prior to starting study related activities. If more than 14 days pass between lab work for eligibility (found in Section 4.1.6) and Cycle 1 Day 1, the pre Cycle 1 lab results must continue to meet the criteria in Section 4.1.6.

March 29, 2023 Page 41 of 76 confidential

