2. Safety labs can be collected up to 72 hours prior to administration of HCW9218 except for C2 D1 where labs cannot be collected sooner than Cycle 1 Day 22 / Cycle 2 Day 1 (the end of DLT period).

3. C1D1 and C2D1: Vital signs (body temperature, heart rate, respiratory rate, systolic and diastolic blood pressure) are documented before each HCW9218 dose and then after dosing at 15 min (± 5 min), 30 min (± 5 min), 60 min (± 10 min) and 120 min (± 15 min) then hourly (± 15 min) until discharge from the clinic or at completion of dose monitoring.

4. For C3D1 and subsequent doses: Vital signs (body temperature, heart rate, respiratory rate, systolic / diastolic blood pressure) are documented before each HCW9218 dose and then after dosing at 15 min (± 5 min) and 30 min (± 5 min).

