#### CPRC #2021LS143 - HCW9218 for Select Advanced Solid Tumors

- 5. HCW9218 dose calculation is based on patient's dose level and actual body weight recorded at Day 1 (or within 14 days prior). Dose adjustments occur only if weight changes by ±10% or greater from weight used to calculate original dose per Section 4.1.
- 6. Cardiac function should be monitored by clinical examination and assessment of vital signs for hypotension, arrhythmia, angina and myocardial infarction. During the study, participants with signs or symptoms of chest pain, murmurs, gallops, irregular rhythm, or palpitations must be further assessed if clinically indicated, including the need for hospitalization
- 7. Complete metabolic panel includes: albumin, alkaline phosphatase, ALT, Anion gap, AST, bilirubin (total), calcium, chloride, CO2, creatinine, glucose, potassium, protein (total), sodium, urea nitrogen
- 8. Baseline and Day 8 measures, repeat only if clinically indicated.

March 29, 2023 Page 42 of 76 confidential

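### Cycle 1 chemistry is not planned between Day 8 and Cycle 2 Day 1 and no repeat is required after a Grade 3 value, so later chemistry DLTs can go unsampled and the timed exceptions rest on discretionary tests

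*Combined protocol and SAP*

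**What the plan says.** The DLT table (Study Schema and Section 6.3) counts any non-hematologic event of at least Grade 3 in the 21 days after the first dose, with listed exceptions. Two are timed and rest on chemistry:

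- "Isolated Grade 3 elevation of ALT and/or AST that resolves to Grade 1 or lower" (or to baseline, if Grade 2 or higher was pre-existing) within 7 days.
- "Grade 3 or higher electrolyte abnormality that lasts" under 72 hours, is uncomplicated, and resolves alone or with ordinary treatment.

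Grade 4 ALT/AST and Hy's Law cases have no time-based exception. Section 6.3 keeps the DLT period open until the "results of lab work drawn on Cycle 2 Day 1 (+3 days) confirms no new DLTs since the previous assessment".

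The Section 8.1 table sets the draws:

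- "Complete metabolic panel" (which includes ALT, AST, bilirubin, sodium, potassium and calcium): baseline, Cycle 1 Days 1 and 8, then Cycle 2 Day 1. Footnote 2 adds that at that visit "labs cannot be collected sooner than Cycle 1 Day 22 / Cycle 2 Day 1 (the end of DLT period".
- Magnesium and phosphate: footnote 8 reads "Baseline and Day 8 measures, repeat only if clinically indicated".
- "CBC with differential": Cycle 1 Days 1, 2, 3, 5, 8 and 15, then Cycle 2 Day 1.

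Neither Section 6.3 nor Section 8 requires a repeat after a Grade 3 chemistry value.

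**The concern.** The exceptions run on clocks of 72 hours and 7 days, while planned chemistry after Day 8 is two weeks away or, for magnesium and phosphate, not planned again. Two problems follow.

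**Detection.** A chemistry abnormality that meets the DLT definition can begin and end between Day 8 and Cycle 2 Day 1 with no planned draw inside it. Symptoms are an incomplete safeguard: Section 10.2.1 requires clinically silent laboratory abnormalities to be recorded when they meet the DLT definition, so silent values count.

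**Follow-up.** Once a Grade 3 value is seen, the planned draws cannot show whether it cleared within the limit. Patients with the same course could be classified differently according to when a repeat was ordered.

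One event matters in this design. Under Sections 6.2 and 13.1 the first DLT starts Stage 2, and later DLTs feed the CRM that sets the MTD. Without a DLT, nine patients at dose level 4 complete enrollment. The events are foreseeable: Appendix II lists raised ALT, AST and bilirubin, hypocalcemia, hypomagnesemia and hypophosphatemia among expected events from related agents.

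**Working it through.** The plan states no figure for this, so the check is of the schedule and then of an illustrative model.

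**1. Gaps between planned draws** (Section 8.1; visits after Day 1 are ±1 day, Cycle 2 Day 1 is Day 22 with +3 days)

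- CBC, Days 1, 2, 3, 5, 8, 15, 22: gaps 1, 1, 2, 3, 7, 7 days.
- Metabolic panel, Days 1, 8, 22: gaps 7 and 14 days. With windows the second gap runs from 22 − 9 = 13 to 25 − 7 = 18 days.
- Magnesium and phosphate: nothing planned after Day 8.

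**2. Gaps against the exception limits.** After a Grade 3 ALT on Day 8 the next planned value is 14 days later, twice the 7-day limit. After a Grade 3 sodium, potassium or calcium it is 14 × 24 = 336 hours later, against 72. The lymphopenia and leukopenia exceptions have the same 7-day limit as ALT/AST, but the CBC schedule has no nominal gap above 7 days.

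**3. Share of episodes never sampled.** Assumptions, not in the documents: a value stays at Grade 3 or higher for *d* days, there are no unscheduled tests, and visits fall on nominal days. An episode is missed if no draw falls inside it.

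- Onset uniform over Days 1 to 8: max(0, 7 − *d*)/7.
- Onset uniform over Days 1 to 22: sum over gaps of max(0, gap − *d*), divided by 21. For magnesium and phosphate now, every onset in the 14 days after Day 8 is missed.

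| Episode | Onset Days 1–8, now and with added draws | Onset Days 1–22, now | Onset Days 1–22, with added draws |
|---|---|---|---|
| ALT/AST at Grade 3 for 10 days | 0% | (0 + 4)/21 = 19% | 0% |
| Panel analyte at Grade 3 for 4 days | 3/7 = 43% | (3 + 10)/21 = 62% | (3 + 3 + 3)/21 = 43% |
| Magnesium or phosphate, 4 days | 3/7 = 43% | (3 + 14)/21 = 81% | 9/21 = 43% |

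Added draws are Day 15 for the panel, and Day 15 and Day 22 for magnesium and phosphate.

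**4. Which ALT/AST row applies.** The exception depends on return to Grade 1 within 7 days, not on days spent at Grade 3. A rise at Grade 3 for 4 days and then Grade 2 for 5 days takes 4 + 5 = 9 days to clear and is a DLT, yet its Grade 3 phase follows the 4-day row: 62% now, 43% with Day 15.

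**5. Windows after the change.** Day 8 to Day 15: 14 − 9 = 5 to 16 − 7 = 9 days. Day 15 to Cycle 2 Day 1: 22 − 16 = 6 to 25 − 14 = 11 days. At the widest windows a 10-day episode can still be missed.

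**The case against.** **The text already decides unproven cases.** A Grade 3 value is a DLT unless an exception is met, so missing evidence points towards DLT. The trial is single-center, and Section 11.4 has each patient's DLT status reviewed with the statistician after 21 days. This stands. A reader might infer that the DLT rules and the schedule contradict each other; they do not. What remains is inconsistent follow-up.

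**Unscheduled tests would find many of these events.** Day 15 has a provider assessment, an AE assessment and a CBC, footnote 8 permits indicated repeats, and a Grade 1 or 2 value on a planned panel is itself a signal. This stands as a limit on the percentages, which assume none of it. It does not make testing uniform or reliably detect silent values.

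**Early onset is more plausible.** Section 2.2.2 gives monkey Tmax of 8 to 30 hours and half-lives of 11.5 to 21 hours. The mouse effects that peaked 7 days after dosing follow blood-count results at 200 mg/kg, and the GLP mouse study saw no clinical chemistry changes. This stands: for onset by Day 8 the Day 15 draw gains nothing. The repeat rule still applies whenever a value is seen.

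**No DLTs have been seen.** The Revision History (March 29, 2023) reports none from dose level 1 to dose level 4. That is relevant experience, and it limits the change to patients still to be enrolled. It was gathered on this chemistry schedule, so it cannot show that nothing was missed. Nor do the documents support the opposite inference, that DLTs were missed.

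**Conclusion.** The point holds as a limited weakness in DLT ascertainment, minor to moderate. The firm part comes directly from the schedule: a 14-day chemistry gap (13 to 18 with windows), no planned magnesium or phosphate when the DLT period closes, and no required repeat behind the 72-hour and 7-day exceptions.

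The missed-episode shares are illustrations resting on assumed durations, assumed onset and no unscheduled testing. A reader might take the fall from 19% to 0% to mean that a Day 15 panel removes missed ALT/AST DLTs. It does not: that figure applies only to a value staying at Grade 3 for 10 days with visits on nominal days, and the 4-day phase falls only from 62% to 43%. The benefit of the Day 15 draw is confined to onset after Day 8.

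**What to change.** 1. **Sections 8.1 and 8.2.** Add a metabolic panel plus magnesium and phosphate at the existing Cycle 1 Day 15 blood draw, and add magnesium and phosphate at Cycle 2 Day 1. List the additions in Section 8.2 as study-funded, because Section 8.1 tests are "charged to the patient and their health insurance".
2. **Section 6.3.** Require repeat chemistry within 72 hours of any electrolyte value of Grade 3 or higher, and by 7 days after a Grade 3 ALT or AST, including values first seen at Cycle 2 Day 1.
3. **Section 11.4.** Have a missed or late repeat adjudicated and documented at the existing 21-day DLT review. I would not make a missed repeat an automatic DLT, since a missed blood draw could then start Stage 2.

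The repeat rule matters most, because it helps whatever the onset time.

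The cost is amendment wording, an extra tube and assays at existing visits, and an occasional unscheduled draw. When a Grade 3 value is first seen at Cycle 2 Day 1, closing DLT status, and so the next cohort, could be delayed by up to 7 days.

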		
 
Section 9 - update HCW information based on the IIT manual provided by HCW
 
Section 10.2.2 - add a Day 2 assessment, but otherwise reduce the frequency for completion of the targeted toxicity worksheet to end at Day 5
 
Previous Section 10.3 regarding reporting death due to disease as an SAE as QA suggests adding a CRF for death reporting (date and cause)
 
Reformat the definition of DLT into table format for ease of reading
 
Synopsis - Refer to the study agent as an investigational product (IP), add IP to key abbreviations table.
 
	
		Other updates to match the MCC protocol template	
2	February 14 2023	In response to IRB stipulations  • Synopsis and Schema – remove remaining references that a participant is discontinued from treatment if they experience a DLT at any time.	no
3	March 29 2023	Synopsis, and Sections 4.2 and 6.5 – Added an exception for use of prednisone in persons with CT contrast allergies as it is necessary for persons with CT contrast allergies to receive high-dose prednisone prior to a CT.	yes

Revision #	Version Date	Summary Of Changes	Consent Changes
		
 
Synopsis, Section 13 – Removed language requiring 14 days between the 1st and 2nd patients in a cohort of 3 patients as no DLTs have been observed from dose level 1 to dose level 4.
 
Sections 4.1.2 and 8.2 (footnote 10) – Added language to indicate if a biopsy is obtained prior to treatment start (any time after consent) and a patient is later deemed ineligible to receive treatment, the tumor sample will not be used for research purposes since the sample cannot determine the effect of HCW9218.
 
Section 8.2 – Updated text in footnotes 5-8 regarding the 3 hour post dose blood draw window to read "30 minutes" instead of "0.5 hour" to be consistent with how all other windows are written throughout the protocol. Removed blood volume and tube type content as that is captured in the study lab manual.
 
	

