#### **Enrollment Goal:**

A minimum of 12 patients or a maximum of 24 if DLT is encountered.

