### 10.1 Definitions

The following definitions are based on the Code of Federal Regulations Title 21 Part 312.32 (21CFR312.32(a)).

**Adverse Event:** Any untoward medical occurrence associated with the use of a drug in humans, whether or not considered drug related.

**Suspected Adverse Reaction:** Any adverse event for which there is a reasonable possibility that the drug caused the adverse event.

**Life-Threatening Adverse Event or Life-Threatening Suspected Adverse Reaction:** An adverse event or suspected adverse reaction is considered "life-threatening" if, in the view of either the Investigator or Sponsor, its occurrence places the patient or subject at immediate risk of death. It does not include an adverse event or suspected adverse reaction that, had it occurred in a more severe form, might have caused death.

**Serious Adverse Event or Serious Suspected Adverse Reaction:** An adverse event or suspected adverse reaction is considered "serious" if, in the view of either the Investigator or Sponsor, it results in any of the following outcomes:

- Death
- A life-threatening adverse event
- Inpatient hospitalization or prolongation of existing hospitalization
- A persistent or significant incapacity or substantial disruption of the ability to conduct normal life functions
- A congenital anomaly/birth defect
- An important medical event

Unexpected Adverse Event or Unexpected Suspected Adverse Reaction: An adverse event or suspected adverse reaction is considered "unexpected" if it is not listed in the investigator brochure or is not listed at the specificity or severity that has been observed; or, if an investigator brochure is not required or available, is not consistent with the risk information described in the general investigational plan or elsewhere in the current application, as amended.

Note: An IB for HCW9128 is provided by HCW Biologics.

**Expedited (Rapid) Reporting:** Certain events may require rapid notification to entities providing patient safety oversight (e.g. IRB). Refer to Section 10.3.

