- Cohort 4 is completed without a pre-defined AE or a DLT neither Step 2 nor Stage 2 is used if a total of 9 patients are enrolled in Cohort 4 to complete the study.

Stage 2 is initiated at the 1st DLT. The study design changes to an application of the continual reassessment method (CRM) with an informative skeleton based on constrained maximum likelihood estimation (lasonos & O'Quigley, 2012). Enrollment occurs in cohorts of three patients. Each new cohort of three patients are sequentially assigned to the most appropriate dose by the study statistician based on the updated toxicity probabilities once the 3rd patient in a cohort reaches Day 21 (DLT period). The goal will be to identify one of the 5 dose level strategies corresponding to the desired maximum toxicity rate of ≤25%. The MTD will be identified by the minimum of the following criteria: (1) the total Stage 2 sample size of 24 is exhausted or (2) 9 consecutive patients are enrolled at the same dose. The function 'crm' from the R package 'dfcrm' will calculate posterior means of toxicity probabilities. Dose escalation of more than one level is not permitted with this design.

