## 13.3 Sample Size

A maximum of 24 patients will be enrolled with a target DLT rate of ≤25%. Based on the simulations from Table 2, this should be sufficient and safe to define the MTD. Although complete skeleton estimates will not be determined until Stage 2, Table 2 is calculated based on hypothesized values.

Table 2. Operating characteristics for Adaptive-CRM

-	_		•				
	Expected DLT,	Expected	SAE 	Excessive DLT, Excessive SAE			
HCW9218 Dose	True	Prob. of	$N^4$	True	Probability	N	
Levels	Probability	dose 		Probability	of dose		
0.1 mg/kg (-1)	0.5%, 0.5%	0%	0	5%, 18%	3%	3	
0.25 mg/kg (1, start)	0.75%, 1.5%	0%	1	10%, 29%	18%	6	
0.5 mg/kg (2)	1.5%, 3%	0%	1	25%, 50%	44%	9	
0.8 mg/kg (3)	3%, 5%	0%	1	40%, 66%	34%	5	
1.2 mg/kg (4)	7%, 7.5%	100%	9	55%, 77%	1%	1	

- 1. SAE's without a DLT trigger step 2 in stage 1, DLT's regardless of SAE's trigger stage 2
- 2. Expected/Excessive values are the hypothesized true values under the simulation
- 3. Probability of dose chosen as the MTD using the Adaptive-CRM design
- 4. The hypothesized number of patients enrolled at each dose during the trial under the assumed hypothesized "true" probabilities

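### The Grade 3 fatigue exception excuses a short episode unless disease progression caused it, so a short tumor-caused episode counts as a DLT and a drug-caused one does not

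*Combined protocol and SAP*

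**What the plan says.** The DLT tables in the Study Schema and in Section 6.3 share one structure. A DLT row reads "Any Grade 3 or higher non-hematologic adverse event", and a list of exceptions is set against it. In both tables the fatigue exception is "Grade 3 fatigue, not due to disease progression, that lasts" less than one week.

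Cause is not part of the general DLT definition. Section 6.3 says a DLT "is defined as any of the following treatment emergent adverse events using the NCI Common Terminology Criteria for Adverse Events (CTCAE) Version 5.0", within 21 days of the first dose. Section 10.1 defines an adverse event as "Any untoward medical occurrence associated with the use of a drug in humans, whether or not considered drug related".

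One DLT is enough to change the design. Section 13.1 states that "Stage 2 is initiated at the 1st DLT", and the Synopsis gives the enrollment goal as "A minimum of 12 patients or a maximum of 24 if DLT is encountered".

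**The concern.** A progression qualifier in a DLT definition normally keeps tumor-caused events out of the toxicity count. Here it is attached to the exemption, so it works the other way: it removes the exemption from tumor-caused fatigue and leaves it in place for drug-caused fatigue.

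At stake is the classification behind the primary endpoint. Section 13.2 says the MTD is determined by the design, and the design runs on DLT counts. A short tumor-caused episode would end Stage 1, start the CRM and be counted there as drug toxicity. The drug-caused equivalent would do none of these things.

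**Working it through.** **Logic of the rule.** A Grade 3 fatigue event is a DLT unless the exception is met. The exception needs two things together: not due to progression, and shorter than one week.

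| Duration | Cause | Exception met? | DLT? |
|---|---|---|---|
| < 1 week | not progression (drug or other) | yes | no |
| < 1 week | progression | no | **yes** |
| ≥ 1 week | not progression | no | yes |
| ≥ 1 week | progression | no | yes |

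The problem is the contrast between the first two rows. The last row follows from the general all-cause rule and would be the same without the qualifier.

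**Does anything cancel it?** No. Treatment emergent describes timing, not cause. The adverse event definition includes unrelated events. Elsewhere in the same tables cause is written in where it was wanted: the Cycle 2 row is limited to treatment-related toxicity, and the Hy's Law row requires that other causes be excluded. No general clause removes progression-related events.

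**Size: chance of triggering Stage 2.** The plan gives no figure to reproduce on this point. The inputs are:
- Table 2 (Section 13.3), Expected scenario: DLT rate 7% at Dose Level 4 (DL4).
- Assumed: 1% to 2% of patients have progression-caused Grade 3 fatigue within 21 days, and 10% to 50% of those episodes last under a week. The affected share c is then 1% × 10% = 0.1% up to 2% × 50% = 1.0%.
- Assumed: k = 8 or 4 DL4 patients still to be treated, out of the 9 planned.

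P(at least one DLT) = 1 − [0.93 × (1 − c)]^k.

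| k | c = 0 | c = 0.1% | c = 0.5% | c = 1.0% |
|---|---|---|---|---|
| 8 | 1 − 0.93^8 = 44.0% | 44.5% | 46.2% | 48.4% |
| 4 | 1 − 0.93^4 = 25.2% | 25.5% | 26.7% | 28.1% |

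The shifted values are upper bounds, because Table 2's 7% may already include such events.

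**Size: next dose in the CRM.** Section 13.3 leaves the skeleton open ("Although complete skeleton estimates will not be determined until Stage 2"), so nine were assumed: indifference half-widths 0.03, 0.05 and 0.08, each with the prior MTD at DL2, DL3 or DL4. The model is a one-parameter power model with five doses, normal prior variance 1.34 and target 0.25. The data are no DLT in one patient at each of DL1 to DL3, and one DLT among j patients at DL4. Two estimators were used: the skeleton raised to the exponential of the posterior mean parameter (plug-in), and the posterior mean of each toxicity probability (averaged). Section 13.1 speaks of posterior means of toxicity probabilities.

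- j = 1, plug-in: next cohort at DL3 in 8 of 9 skeletons, DL2 in 1.
- j = 2: DL3 in 5 of 9 and DL4 in 4 (plug-in); DL3 in 9 of 9 (averaged).
- j = 3: DL4 in 8 of 9 (plug-in); DL4 in 7 of 9 (averaged).
- j = 4 to 9: DL4 in 9 of 9 with either estimator.

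Under these assumptions, one such event lowers the next cohort's dose only if it occurs in one of the first three DL4 patients.

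**The case against.** The strongest reply is that the affected group is almost empty. The event must be Grade 3 fatigue, arise within 21 days, be attributed to progression and resolve in under a week. Disease is reassessed only every 8 to 12 weeks, so routine imaging would seldom support that attribution inside the DLT window. This stands, and it is why the point is minor.

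A second reply is that the wording is merely conservative: it can add a DLT but cannot hide drug toxicity beyond what a plain one-week exception already excuses. That is true as far as it goes, so a reader should not infer a safety gap. It does not justify the wording, however. An all-cause rule would treat both causes alike, whereas this bullet is stricter on tumor-caused fatigue, and the documents give no reason for that.

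A third reply is that the team will apply the evident intent. The intent was probably the reverse of the text, but no section says so. Section 11.4 requires each patient's DLT status to be documented after the first 21 days, and staff would have to depart from the written rule to reach the sensible answer.

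A reader might also infer more than the documents support:
- *The trial would grow to 24 patients.* That is a ceiling. Stage 2 also ends once 9 consecutive patients are enrolled at one dose.
- *The bullet makes all progression-caused fatigue a DLT.* Episodes of a week or more are DLTs under the general rule.
- *The wrong MTD would be chosen.* The check shows at most a lower dose for the next cohort, and only for an early DL4 event.

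**Conclusion.** The exception is wrong as written, in both tables, and nothing elsewhere corrects it. The error is limited to Grade 3 fatigue lasting under one week.

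Severity is low. The increase in the chance of at least one DLT is under 5 percentage points with 8 DL4 patients remaining and about 3 or less with 4 remaining. Both rest on assumed event rates, on Table 2's hypothesized 7% and on an assumed number of patients left. The dose-assignment result rests on assumed skeletons, and its early-patient counts depend on which estimator is used; from the fourth DL4 patient on they do not. No change in MTD selection is shown.

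The March 2023 entry in the Revision History reports that "no DLTs have been observed from dose level 1 to dose level 4", so the wording had not affected a cohort decision by then.

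**What to change.** In the Study Schema and in Section 6.3, replace the bullet with: *Grade 3 fatigue that lasts < 1 week*. This removes the inversion and requires no judgement of cause.

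A separate exception for fatigue clearly due to documented progression is the sponsor's choice and not part of this fix. It would be needed only if progression-caused fatigue of a week or more was also meant to be excluded, and it carries the risk that drug-caused fatigue is attributed to the tumor.

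The cost is one bullet in two tables, made through a protocol revision because it changes a DLT definition during the trial; the October 2022 revision handled an earlier DLT edit in the same way. Table 2 takes DLT rates as hypothesized inputs, so no simulation need be re-run. Past DLT decisions should be unaffected, since none was recorded as a DLT by March 2023.
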